7.4 Medical History

Medical history (other than acne history) will be summarized by Medical Dictionary for the Drug Regulatory Activities (MedDRA) System Organ Class and Preferred Term for the Safety population. One subject will be counted once for each applicable Preferred Term and System Organ Class. MedDRA version 25.0 will be used.

Medical history data will also be listed.

7.5 Protocol Deviations

Protocol deviations will be recorded in the eCRF during the study and identified programmatically. The deviations that are identified programmatically and the algorithms for their identification are defined in a separate Programmed Protocol Deviations Specification.

[REDACTED]

All major protocol deviations will be summarized by deviation category and treatment group. This analysis will be performed for the mITT population.

All protocol deviations will be listed.

7.6 Efficacy Analyses

7.6.1 Center pooling

To eliminate potential effect of random fluctuations at small site on the primary endpoints small centers will be pooled. [REDACTED]

[REDACTED]

[REDACTED]

[REDACTED]

[REDACTED]

[REDACTED]

[REDACTED]

Pooled centers will be used in all ANOVA models, including the efficacy analyses and the comparison of the treatment group in the summary of the demographic and baseline characteristics.

7.6.2 Analyses of Primary Endpoint

At each study visit, beginning at Visit 1, an Investigator will count the number of open and closed comedones (non-inflammatory lesions), pustules and papules (inflammatory lesions) and nodulo-cystic lesions. Lesion counts will be recorded in the CRF.

Missing Week 12 assessments will be imputed as follows. In the mITT analysis, if a subject discontinues the study prior to Week 12 or misses the Week 12 assessment for any other reason, the LOCF rule will be used to impute the number of lesions. In the PP analysis, if a subject discontinues the study prior to Week 12 due to lack of treatment effect [REDACTED], the LOCF rule will be used to impute the number of lesions. If a subject is missing the Week 12 assessment for any other reason, the subject will be excluded from the PP population.

The LOCF rule will be applied as follows: the last available post-baseline lesion count of the given type will be carried forward to impute the missing Week 12 assessment of the same type. Subjects who do not have any post-baseline lesion counts of a certain type will be excluded from the analysis of that type.

The baseline lesion count will be defined as the results from the latest examination prior to the first application of the study medication. For each post-baseline visit the change from baseline and percent change from baseline in the number of inflammatory and non-inflammatory lesions will be calculated. The baseline value, visit value and percent change from baseline at the visit will be analyzed using descriptive statistics and will be tabulated by visit and treatment group.

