5.1.5 Subject Disposition and Discontinuation

All Subjects are free to withdraw from participation in the study at any time, for any reason, specified or unspecified, and without prejudice to further treatment. The criteria for enrollment are to be followed explicitly. Investigators are urged to enroll only those eligible Subjects who are likely to complete the entire study and who are willing to comply with the protocol-specified procedures. It is the right and duty of the investigator to interrupt the treatment of any Subject whose health or well-being may be threatened by continuation in this study, or who may be experiencing unmanageable factors that may interfere with the study procedures and/or the interpretation of study results. Such Subjects should be withdrawn from the study rather than continued under a modified regimen. The reason for withdrawal or discontinuation from the study will be documented appropriately.

In addition, investigational product will be stopped, and Subjects will be discontinued from the study for any of the following reasons:

- a. If the Subject withdraws his or her consent/assent for any reason.
- b. Subjects who are discontinued early from the study due to lack of treatment effect should be included in the PP population as treatment failures, using Last Observation Carried Forward (LOCF).
- c. If the Subject's acne condition has worsened beyond grade 4 or to the degree that the Principal Investigator feels it is unsafe for the Subject to continue in the study, the subject should be discontinued, but included in the mITT and PP population analysis using LOCF and provided with effective rescue treatment for exacerbation of their acne.
- d. 
- e. If the Subject has a SAE.
- f. If the Subject's drug code is unblinded.
- g. If an adverse event occurs for which the Subject desires to discontinue treatment or the Principal Investigator determines that it is in the Subject's best interest to be discontinued.
- h. If there is a significant protocol deviation if it affects the safety or well-being of the subject.
- i. 
- j. If a concomitant therapy is reported or required which is liable to interfere with the results of the study.
- k. If the Subject is lost to follow-up.
- l. If the Subject becomes pregnant.
- m. If the Subject becomes a prisoner or becomes involuntarily incarcerated.
- n. Any other reason that may affect the outcome of the study or the safety of Subjects; or
- o. Termination of the study by the Sponsor.

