6.6 Lack of Treatment Effect (LOTE)

After completion of at least 4 weeks of the treatment period, if the subject comes to the Investigator and informs about not observing the desired treatment effect, then Investigator will evaluate the lesion counts and IGA scores and judge the lack of treatment effect. If the subject makes the decision to withdraw or discontinue from the study, then the reason for withdrawal/discontinuation will be coded as “lack of treatment effect (LOTE).”

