8.7 Early Termination of a Subject

A subject may terminate from the study early for any reason at any time without any disadvantages. In this case, the Investigator should make every effort to have the subject return to the next scheduled visit to perform all required Early Termination (Early Discontinuation) visit activities and to collect and reconcile all study IMP. If the subject does not return for the Early Termination (Early Discontinuation) visit, the site should fully document the reason for early termination. All data, including the date and primary reason for termination, must be recorded on the Early Termination (Early Discontinuation) case report form (CRF), and source document.

Any subject who experiences an adverse event may be terminated from the study or from study treatment at any time at the discretion of the Investigator. In this case, the subject should be followed at the discretion of the Investigator until the resolution or stabilization of the AE. All applicable data should be recorded in the adverse events section of the case report form (CRF). If a subject terminates from the study early for multiple reasons that include adverse events, the Early Termination (Early Discontinuation) case report form should indicate that early termination was related to an adverse event.

An exception to this requirement will be the occurrence of an adverse event that in the opinion of the investigator is not severe enough to warrant early termination but that requires the use of a prohibited medication, thereby requiring discontinuation of the subject. In such a case, the reason for discontinuation would be needed to take a prohibited medication, not the adverse event.

The Investigator must inform the Medical Monitor and CRO as soon as possible of all subjects who are being considered for early termination due to adverse events. Additional reports must be provided when requested. The CRO will inform the Sponsor of this event.

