10.2 Datasets to be Analyzed

Three analysis populations will be used in the analysis of the clinical data:

[Redacted]

[Redacted]

[Redacted]

[Redacted]

[Redacted]

[Redacted] proper administration of the treatment or accurate evaluation of its effectiveness.

[Redacted]

[Redacted]. In addition, subjects whose condition or symptoms worsens and require alternate or supplemental or rescue therapy for the treatment of their condition during the treatment phase of the study should be discontinued, included in the mITT and PP population analysis using LOCF, and provided with effective treatment. The use of supplemental medicines and rescue medicine will be per standard of care (SOC) per medical judgement of the Investigator. All supplemental and rescue medicines will include name, dose, frequency of administration, start and end dates, which is supplied to discontinued subjects for worsening of conditions.

[figure not shown]
[Redacted]

[Redacted]

[Redacted] If subject makes the decision to withdraw or discontinue from the study, then the reason for withdrawal/discontinuation will be coded as “lack of treatment effect” (LOTE).

[Redacted]

A shift table will be provided for any subject that has been discontinued with the reason of lack

of treatment effect to show changes from screening/baseline to time of discontinuation (last observation).

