6.3 Per Protocol Population (PP Population)

[REDACTED]

- [REDACTED]
- [REDACTED]
- [REDACTED]
- [REDACTED]
- [REDACTED]
- [REDACTED]

Subjects who are discontinued early from the study due to lack of treatment [REDACTED] will be included in the PP population as treatment failures (i.e., non-responders) even if they do not have Week 12 evaluation within the visit window or at all. A “last observation carried forward” (LOCF) approach will be used for imputing missing lesion counts in these PP subjects.

Per protocol, subjects whose condition or symptoms worsens and require alternate or supplemental or rescue therapy for the treatment of their condition during the treatment phase of the study should be discontinued, included in the mITT and PP population analysis using LOCF, and provided with effective treatment. The reason for study discontinuation for these subjects should be set to “Lack of treatment effect”, therefore for practical purposes this group of subjects is a subgroup of subjects who are discontinued early from the study due to lack of treatment effect.

[REDACTED]

The PP population will be considered as definitive for testing the clinical equivalence and as supportive while testing the superiority. Subjects will be analyzed according to the treatment they were randomized to receive.

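### A subject discontinued for severe acne worsening and recorded as an adverse event under Protocol 8.7 is kept in PP by SAP 6.3 but, by recorded reason, excluded by SAP 7.6.2

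*SAP*

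**What the plan says.** PP is definitive for equivalence (SAP 6.3), and SAP 7.6.2.1 schedules the bioequivalence analysis on PP only.

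The protocol keeps treatment failures in that set. For acne that has worsened beyond grade 4 or to an unsafe degree, Protocol 5.1.5 item c says "the subject should be discontinued, but included in the mITT and PP population analysis using LOCF". For subjects who worsen and need alternate, supplemental or rescue therapy, Protocol 10.2 says they are to be discontinued, "included in the mITT and PP population analysis using LOCF, and provided with effective treatment". Neither passage attaches a reason code in its readable text.

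SAP 6.3 restates the inclusion and adds a coding rule: "The reason for study discontinuation for these subjects should be set to" lack of treatment effect (LOTE). From this it concludes that "for practical purposes this group of subjects is a subgroup of subjects who are discontinued early" for LOTE.

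SAP 7.6.2 then sets the imputation. In mITT, LOCF fills every missing Week 12 count. In PP, LOCF applies to discontinuation due to LOTE, followed directly by a redaction. The closing sentence is: "If a subject is missing the Week 12 assessment for any other reason, the subject will be excluded from the PP population".

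Protocol 8.7 says that when a subject stops for several reasons that include adverse events, the "case report form should indicate that early termination was related to an adverse event". Protocol 11.1 counts significant worsening of the disease under study as a possible adverse event, but only when its presentation or outcome is more severe than expected for that subject.

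**The concern.** Whether a worsened subject stays in PP appears to depend on a discontinuation code that the site enters, and Protocol 8.7 can direct the site to a code other than the one SAP 6.3 expects. The most severe worsenings are the ones most likely to qualify as adverse events, so any exclusion would depend on outcome. It would fall on the definitive equivalence set, where a failure removed from one arm pulls that arm's mean towards its non-failures. The analyst would also have to choose between two SAP sections, which a SAP should make unnecessary.

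**Working it through.** **Step 1. Text.** Take a subject whose acne worsens severely enough to be an adverse event, who is discontinued for it, and who has no Week 12 count.

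| Source | Result for this subject |
|---|---|
| Protocol 5.1.5 item c, Protocol 10.2 | In PP by LOCF |
| SAP 6.3 | In PP by LOCF; reason to be LOTE |
| Protocol 8.7 with 11.1 | Form shows adverse event |
| SAP 7.6.2, applied by recorded reason | Not LOTE, so excluded from PP |

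SAP section 8 declares no change from the protocol analyses except the mITT definition, so nothing readable resolves the conflict.

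**Step 2. Size of the effect on the ratio.** There is no plan figure to reproduce: the sample-size assumptions are redacted (Protocol 10.1.1, SAP 3.2), and the documents give no failure or coding rates. Every input below is an assumption.

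- mu: mean percent change in non-failures, -50 or -60, the same in both arms
- f: carried-forward percent change in failures, 0, +20 or +50
- p: proportion failing in the arm
- m: fraction of failures not recorded as LOTE and therefore dropped

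Arm mean = [(1-p)·mu + (1-m)·p·f] / (1 - m·p). The shift is the Test/Reference ratio at m minus the ratio at m = 0.

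Worked case: 4% vs 2% failing, mu = -50, f = +50, m = 0.5.

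- All kept: Test 0.96(-50) + 0.04(50) = -46; Reference 0.98(-50) + 0.02(50) = -48; ratio 0.9583.
- Half dropped: Test (-48 + 1)/0.98 = -47.96; Reference (-49 + 0.5)/0.99 = -48.99; ratio 0.9790.
- Shift +0.0206.

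Ranges over all mu and f:

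| Failing, Test / Reference | 25% dropped | 50% dropped | All dropped (ceiling) |
|---|---|---|---|
| 2% / 1% | +0.0025 to +0.0051 | +0.0050 to +0.0102 | +0.0101 to +0.0204 |
| 1% / 2% | -0.0025 to -0.0053 | -0.0051 to -0.0105 | -0.0102 to -0.0208 |
| 4% / 2% | +0.0049 to +0.0103 | +0.0100 to +0.0206 | +0.0204 to +0.0417 |
| 2% / 4% | -0.0051 to -0.0111 | -0.0103 to -0.0220 | -0.0208 to -0.0435 |
| 3% / 3% | 0 | 0 | 0 |

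With 3% failing in each arm but half of one arm's failures dropped and none of the other's, the shift is +0.0152 to +0.0314 (Test dropped) or -0.0150 to -0.0305 (Reference dropped).

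**Step 3. Can a verdict change?** The trial's own confidence interval cannot be computed without N and SD. As an extreme illustration, the Fieller formula of SAP 11.2 was applied (pooled variance, no centre term) with every failure dropped. Assumptions: 250 or 400 per arm; SD 35; mean reduction in non-failures 55% for Reference and 50%, 51% or 55% for Test; failures carried at 0% or -25% reduction with SD 30; failing 2%/2%, 5%/5%, 4%/1% or 8%/2% (Test/Reference).

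- Equal failing: the ratio moves by at most about 0.002 and no verdict changes.
- Unequal failing: the ratio moves by about 0.03 to 0.09. The verdict changes in 12 of the 48 combinations, all with a lower Test mean in non-failures and more Test failures.
- Example, 50% vs 55% reduction, 4% vs 1% failing, failures at 0%: with 250 per arm, kept 0.882 (0.794, 0.977) fails and dropped 0.909 (0.822, 1.004) passes. With 400 per arm the same case passes both ways: (0.812, 0.956) and (0.840, 0.984).

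The illustration has no combination in which Test fails less often. Step 2 shows that the shift then reverses.

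**The case against.** The strongest reply is that SAP 6.3 does not merely assume the code. It restates the inclusion, prescribes LOTE, and sits in the section that defines PP. The 7.6.2 trigger is discontinuation due to LOTE, not a LOTE entry on a form, so read with 6.3 the subject already qualifies. Protocol sections 3 and 8.5 also describe subjects who worsen to an unsafe degree as treatment failures, the term used for LOTE subjects kept in PP. Text is redacted inside the 7.6.2 trigger, in SAP 6.3 and around the LOTE sentence in Protocol 10.2, and the eCRF instructions are not among the documents. All of this stands. It reduces the point to a conflict for one kind of subject, but does not remove it: the precedence rule in 8.7 is fully readable, and 6.3's step of folding these subjects into LOTE suggests that the plan relies on the code.

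A reader might infer further routes out of PP. The documents do not carry them:

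- Protocol 6.6 says "If the subject makes the decision to withdraw or discontinue from the study, then the reason for withdrawal/discontinuation will be coded as" LOTE, after at least 4 weeks. It does not say that LOTE is used only then.
- The prohibited-medication exception in 8.7 needs an adverse event not severe enough for termination. It hardly overlaps with worsening that itself calls for discontinuation.
- Protocol 5.1.5 lists worsening apart from item j ("If a concomitant therapy is reported or required which is liable to interfere with the results of the study"), but that list gives grounds for stopping and is not a coding instruction.

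On size, the blind makes one-sided miscoding unlikely. mITT, with LOCF throughout, is supportive for equivalence, and SAP 7.2 tabulates exclusions by reason. These would reveal the effect without correcting the definitive set.

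**Conclusion.** One readable conflict holds: Protocol 8.7 with 11.1 against the code in SAP 6.3, which leaves 6.3 and 7.6.2 pointing opposite ways for a worsened subject recorded as an adverse event and without a Week 12 count. It would be too strong to say that the plan excludes worsened or rescued subjects from PP. SAP 6.3 plainly intends to keep them, and hidden text may already do so in 7.6.2.

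The number affected is unknown and probably small. With a quarter to a half of failures dropped, and failure rates of 1% to 4% that differ between arms, the ratio moves by about 0.002 to 0.02 either way. It moves by about 0.03 if coding errors fall in one arm only, and not at all when failures, coding and non-failure means match. Against [0.80, 1.25] this matters only when a confidence limit lies near a bound. The superiority analysis on mITT is unaffected. This is a cheap improvement, between minor and should-fix.

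**What to change.** In SAP 6.3 and 7.6.2, define the PP/LOCF group as discontinuation for LOTE, or for acne worsening or need of alternate, supplemental or rescue acne therapy as in Protocol 5.1.5 item c and 10.2, whatever reason code is recorded. Identify these subjects from data already collected: rescue initiation, IGA including worsening beyond Grade 4, and the discontinuation form. Settle the cases at a blinded review before database lock. Cross-reference 7.6.2 to 6.3, and reconcile the coding passages in Protocol 8.7 and SAP 6.3. If redacted text already does this, confirm it and align the wording of 7.6.2.

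The cost is a few lines of SAP text, a small derivation and a review of a few cases. The PP set may become slightly larger, and the ratio may move slightly in either direction.

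### The carry-forward rule for lesion counts has no cut-off at the start of rescue, so some treatment failures can enter the primary analyses with a post-rescue count

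*SAP*

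**What the plan says.** - **Which count is used.** When Week 12 is missing, SAP 7.6.2 says that "the last available post-baseline lesion count of the given type will be carried forward". The paragraph that states this rule is unredacted. It sets no condition on rescue, last application or days off drug.
- **Superiority (mITT).** SAP 7.6.2 applies the rule broadly: "if a subject discontinues the study prior to Week 12 or misses the Week 12 assessment for any other reason, the LOCF rule will be" (the sentence goes on to the imputation itself).
- **Equivalence (PP).** SAP 7.6.2 limits LOCF to discontinuations for lack of treatment effect, plus a redacted phrase. Anyone else without a Week 12 assessment leaves PP. SAP 6.3 says the lack-of-effect subjects "will be included in the PP population as treatment failures (i.e., non-responders) even if they do not have Week 12 evaluation".
- **Rescued subjects.** Protocol 5.1.5 has worsened subjects discontinued but "included in the mITT and PP population analysis using LOCF and provided with effective rescue treatment for exacerbation of their acne". SAP 6.3 repeats that such subjects "should be discontinued, included in the mITT and PP population analysis using LOCF, and provided with effective treatment", and codes them as lack of treatment effect.
- **Timing of the last assessment.** For early termination, Protocol 8.7 tells the investigator to "make every effort to have the subject return to the next scheduled visit". The schedule in Protocol section 4 includes lesion counts at that visit. Under Protocol 8.5, an unscheduled visit at which a subject is discontinued becomes the Early Discontinuation Visit, with all its procedures. Under Protocol 6.6, the investigator evaluates lesion counts when judging lack of effect.
- **Data available.** Protocol 5.1.5 records the initiation of rescue. Protocol 10.2 adds: "All supplemental and rescue medicines will include name, dose, frequency of administration, start and end dates".

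**The concern.** Carrying a failure's count forward records the failure only if the count was taken before another acne treatment began. The SAP rule does not require that. A subject who stops between visits, starts rescue and returns at the next scheduled visit contributes a count that partly measures the rescue. So does a subject who was counted at the decision to stop and is counted again later, because the later count is then the last one available.

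Both primary decisions use these values. In the definitive PP equivalence analysis, a Test product that fails more often than Reference would look closer to it, which favours concluding equivalence. In the mITT superiority analysis, if Vehicle has more failures, its mean improves and the active-Vehicle difference shrinks; that error is conservative but costs power.

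**Working it through.** The plan gives no figure to reproduce: sample size, means, SDs, allocation and dropout are redacted.

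**Step 1: how late the count can be.** Visits fall on Days 0, 28, 56 and 84. The longest gap is 28 − 0 = 56 − 28 = 84 − 56 = 28 days. Under Protocol 8.7 the final count can therefore fall up to 28 days after the subject stops, plus the redacted window.

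**Step 2: a stop after Visit 3.** The next scheduled visit is Day 84. If that count is treated as an observed Week 12 value, it is used directly. If stopping before Week 12 triggers LOCF, the same count is the last available post-baseline one and is carried forward. Both readings give the same number, so a change confined to imputed values could miss it.

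**Step 3: illustration. Every input is an assumption.** The mean percent reduction in an arm is (1 − f)·m + f·x, where f is the share of failures, m the reduction in non-failures and x the reduction analysed for failures. Take m = 55 for Test and Reference and 40 for Vehicle. Take x = 5 before rescue and 45 after. If a quarter of failures have post-rescue counts, x = 0.75·5 + 0.25·45 = 15.

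*Test/Reference ratio, failures 8% versus 2%:*
- Pre-rescue: (0.92·55 + 0.08·5)/(0.98·55 + 0.02·5) = 51.0/54.0 = 0.944
- A quarter post-rescue: (50.6 + 0.08·15)/(53.9 + 0.02·15) = 51.8/54.2 = 0.956
- All post-rescue: (50.6 + 0.08·45)/(53.9 + 0.02·45) = 54.2/54.8 = 0.989

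*Failures 4% versus 2%:*
- Pre-rescue: 53.0/54.0 = 0.981
- A quarter post-rescue: 53.4/54.2 = 0.985
- All post-rescue: 54.6/54.8 = 0.996

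*Active minus Vehicle, failures 3% versus 10%:*
- Pre-rescue: (0.97·55 + 0.03·5) − (0.90·40 + 0.10·5) = 53.5 − 36.5 = 17.0 points
- A quarter post-rescue: 53.8 − 37.5 = 16.3 points
- All post-rescue: 54.7 − 40.5 = 14.2 points

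**Step 4: range over other assumed inputs.** With non-failures at 45 to 55, failures at −20 to 0 before rescue and 30 to 40 after, and *every* failure affected:

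| Failures, Test vs Reference | Ratio, pre-rescue counts | Ratio, all post-rescue |
|---|---|---|
| 6% vs 3% | 0.955–0.969 | 0.986–0.997 |
| 10% vs 5% | 0.922–0.947 | 0.977–0.994 |
| 15% vs 5% | 0.844–0.895 | 0.953–0.989 |

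For superiority the loss is (f_Vehicle − f_active) × rescue gain. It runs from (0.06 − 0.02)·30 = 1.2 points to (0.15 − 0.05)·60 = 6.0 points, again with every failure affected. The direction is the same throughout; the right-hand column is an upper bound.

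**The case against.** The strongest reply is that the protocol already obtains a count at the decision to stop for most failures. Protocol 6.6 has the investigator evaluate lesion counts before lack of effect is judged. Section 3 describes worsening in the context of Visits 2 to 4, where lesions are counted. Section 8.5 turns an unscheduled visit at which a subject is discontinued into the Early Discontinuation Visit. This stands: exposure is limited to those who stop between visits without a count, or who are counted again after rescue. A reader might infer that treatment failures generally enter with post-rescue counts; the documents do not support that.

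The PP exposure is narrower still, because LOCF there covers only lack-of-effect discontinuations (which SAP 6.3 makes include rescued subjects) plus the redacted phrase. Someone who simply stops for another reason matters mainly in mITT, where the expected error is conservative.

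A reader might also infer that LOCF is bypassed for a subject who stops after Visit 3 and is counted at Day 84. The text does not establish this, since the mITT rule is triggered by discontinuation before Week 12. Step 2 shows that the count analysed is the same either way.

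Finally, the population definitions and parts of Protocol 10.2 and SAP 6.3, 7.5 and 7.6.2 are redacted, so a cut-off there cannot be excluded. The redaction near the PP LOCF sentence sits in the clause on who receives LOCF, however, and not in the rule on which count is carried. If a cut-off exists elsewhere, 7.6.2 should refer to it.

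**Conclusion.** The gap is real. As written, the readable rule can analyse a post-rescue count as the value of a subject meant to be counted as a failure, and the protocol gives different timings for the early discontinuation assessment.

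Its size is unknown and probably small. In the illustration at 8% versus 2% failures, a quarter affected moves the ratio by about 0.01 (51.0/54.0 to 51.8/54.2). The larger shift of 0.045 (0.989 − 0.944) requires every failure to be affected, which the visit rules do not support. The anti-conservative direction for equivalence also requires that Test fail more often than Reference and that rescue act by the time of the count; neither can be established from the documents. This should be fixed, because the rule decides a primary-analysis value and is best settled before unblinding, but it does not by itself undermine the design.

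**What to change.** 1. **SAP 7.6.2.** For subjects discontinued for lack of effect or worsening, or who start rescue or prohibited acne therapy, define the Week 12 value as the last post-baseline count of that lesion type taken on or before the start of that therapy. Apply this even when a later count exists, including one at Day 84.
2. **Later counts.** List them, and use them only in a sensitivity analysis that takes all available counts.
3. **Fallback.** SAP 7.6.2 excludes subjects with no post-baseline count of a given type. Under the new rule, that exclusion could drop a failure rescued before any such count, whom the protocol intends to keep. State a value for this case, for example zero change from baseline.
4. **Protocol.** Reconcile the timing of the early discontinuation assessment in 8.7 with 8.5 and 6.6. Nothing here concerns whether or when rescue is given.

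The cost is a few sentences in the SAP and the reconciliation of those protocol sections. Rescue start dates are already collected. The downside is small: some subjects contribute an earlier visit's count or the fallback value.
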